**Table 5**      **Olaparib Monotherapy Phase – see Section 4.2.3**

Visit Type	Olaparib Monotherapy Phase a						Olaparib Monotherapy Treatment Discontinuation	Post Discontinuation Follow-up
	Monotherapy Day 1 b	Monotherapy Day 8 b	Monotherapy Day 15 b	Monotherapy Day 22 b	Monotherapy Day 43 b	Every 6 weeks	N/A	30 days post discontinuation
Visit Window		± 2 days	± 2 days	± 2 days	± 4 days	± 4d	± 3 days	± 3 days
Physical Exam	X				X	X	X	
Vital signs (Includes BP [supine position], pulse rate (PR), body temperature)	X				X	X	X	X
Performance Status	X				X	X	X	X
ECG c							X	
Haematology / Clinical Chemistry	X	X	X	X	X	X	X	X
Tumour Assessment (CT or MRI according to RECIST) d	Tumour assessments at weeks 9 and 18 (± 1 week) and every 12 weeks (± 1 week) thereafter relative to date of cycle 1 day 1 of the combination therapy until disease progression							
Adverse Events	X	X	X	X	X	X	X	X
Concomitant Medications	X	X	X	X	X	X	X	X
Olaparib dispensed / returned e,f	X				X	X	X	

- a All patients should attend study visits until objective disease progression according to RECIST or the patient must discontinue due to unacceptable toxicity as outlined in the protocol
- b Day is relative to the start of olaparib (AZD2281) monotherapy
- c ECGs performed at baseline, completion of chemotherapy, and discontinuation of olaparib maintenance and if clinically indicated at any other time. ECG should be performed once the patient has been in the supine position for at least 5 minutes in each case.
- d RECIST assessment by CT or MRI scans of chest abdomen, pelvis and other regions including chest as clinically indicated for the assessment of disease. Any other sites at which new disease is suspected should also be appropriately imaged If an unscheduled assessment was performed and the patient has not progressed, every attempt should be made to perform the subsequent assessments at their scheduled visits. Mandatory tumour assessments will be performed at baseline, 9 weeks and 18 weeks and every 12 weeks thereafter relative to date of cycle 1 day 1 of combination therapy until disease progression (At withdrawal, RECIST assessment is required, however if the previous RECIST assessment was performed within 6 weeks of withdrawal, the withdrawal RECIST assessment should be performed but can be missed at the discretion of the investigator.
- e When all other procedures have been performed, olaparib will be dispensed (sufficient for an appropriate number of days/cycles of treatment). Used and unused olaparib should be accounted for and compliance checked. At the discontinuation visit, no olaparib will be dispensed
- f AZD2281 dose administration is not required in clinic

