#### **4.2.3 AZD2281 Monotherapy**

Upon completion of cycle 6 (ie, 21 days after last dose of chemotherapy), cisplatin may be discontinued and AZD2281 alone may be continued at the optimal monotherapy dose (i.e. 400 mg bid) at the investigators discretion.

The first dose of olaparib maintenance (Day 1 of olaparib maintenance phase) is the day after the chemotherapy discontinuation visit.

Following the patients' first dose of olaparib maintenance, they will return to the clinic for safety assessments at days 8, 15, 22 and 43, and then every 6 weeks thereafter relative to monotherapy day1 until objective disease progression as per RECIST criteria (assessed every 12 weeks), unless any other discontinuation criteria are met. See [Table 5](#) for specific assessments and time points.

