- h Patients receiving benefit from treatment with AZD2281 and cisplatin can continue provided they are receiving benefit and are free from intolerated toxicity. Routine safety visits will be performed until discontinuation. Tumour assessments will be performed at the end of every 2 cycles of cisplatin (6 weekly intervals). In the event that cisplatin is permanently discontinued, treatment with AZD2281 alone may continue. If cisplatin is permanently discontinued, patients should have weekly visits for the first two months (8 weeks) of AZD2281 monotherapy, and then every month (4 weeks) after 2 months of AZD2281 monotherapy. After the patients completes 4 cycles of cisplatin at the full dose of 75 mg/m^2, subsequent cycles of cisplatin may be administered at a reduced dose as low as and including 50 mg/m^2 at the investigator's discretion. After patients complete 6 cycles of cisplatin based therapy, cisplatin may be discontinued and AZD2281 alone may be continued at the optimal monotherapy dose (i.e. 400 mg bid) at the investigators discretion. See Section 4.5.2.2 for full details. Note: After protocol amendment 6 is approved, patients on AZD2281 monotherapy can have their visit schedule modified as per Table 5 and Section 4.2.3.
- i Blood samples for AZD2281 PK will be taken relative to the morning dose of AZD2281: predose, 1,2,3,4,6, 8, 12 hrs post dose. A 10 minute time window (+/- 10 minutes) will be allowed but the samples should be taken as close to the nominal time point as possible. If it is not possible to take the 12 hour sample at the correct time, take the sample as close to 12 hours as possible ensuring this sample is taken at the same time at Visit 2 and Visit 3. PK blood draws will not be performed for patients enrolled into an intermittent dosing cohorts.

- j Audiometric testing should be performed at baseline, at the end of the 2nd, 4th and 6th cycles of cisplatin and as clinically indicated thereafter. A final audiogram should be done at study completion. In the event that cisplatin is permanently discontinued, only the final audiometric test done at study completion is required, unless otherwise clinically indicated.

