- p RECIST assessment by CT or MRI scans of chest abdomen, pelvis and other regions including chest as clinically indicated for the assessment of disease. Baseline assessment may be performed up to 28 days prior to study day 1 (see [Appendix D](#)). Follow up assessments performed at the end of every 2 cycles of treatment +/- 1 week (see [Appendix D](#)). Confirmation of response will be at the next scheduled assessment. Once a patient has completed 3 months (12 weeks) of monotherapy, tumour assessments are only required at the end of every 3 months (every 12 weeks (+/- 1 week)). At withdrawal, RECIST assessment is required, however if the previous RECIST assessment was performed within 6 weeks of withdrawal, the withdrawal RECIST assessment should be performed but can be missed at the discretion of the investigator.
- q Until a patient is withdrawn from the treatment or the study the assessments should be carried out as in visits 9/10/11

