#### 4.4.6 Discontinuation of Study Treatment

##### 4.4.6.1 Criteria for Discontinuation from Study Treatment

Patients may be discontinued from investigational product (IP) in the following situations:

- Patient decision. The patient is at any time free to discontinue treatment, without prejudice to further treatment

- Adverse event
- Severe non-compliance to study protocol
- Any CTCAE grade 3 or 4 events that have not reverted to CTCAE grade 1 or less within 28-days. At the Investigator's discretion, following dose interruption, patients may be considered for dose reductions. However, if upon re-challenging with AZD2281 at the lowest reduced dose, (for guidelines refer to Section 4.5.3), any CTCAE grade 3 or 4 adverse events recur, the patient must be discontinued.
- Bone marrow findings consistent with myelodysplastic syndrome/acute myeloid leukaemia
- Disease progression

Note: Patients may continue to receive study treatment following objective progression provided that, in the opinion of the Investigator, the patient is benefiting from the treatment and does not meet any other discontinuation criteria.

In the event that cisplatin is permanently discontinued on the basis of cisplatin related toxicity, treatment with AZD2281 alone may continue. If the patient does continue on AZD2281 alone, at the discretion of the PI and in consultation with AstraZeneca Study Team Physician, the patient may be dose escalated to receive the optimal monotherapy dose (i.e.: 400 mg bid).

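### Section 4.2.3 and Table 5 footnote a end monotherapy safety visits at RECIST progression, although Section 4.4.6.1 lets AZD2281 continue past it

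*Protocol*

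**What the plan says.** Section 4.2.3 brings monotherapy patients back for safety assessments on days 8, 15, 22 and 43 and then every 6 weeks, "relative to monotherapy day1 until objective disease progression as per RECIST criteria", unless another discontinuation criterion is met first. Table 5 footnote a is attached to the heading of the whole monotherapy phase and repeats the rule: "All patients should attend study visits until objective disease progression according to RECIST". Its only alternative end point is discontinuation for unacceptable toxicity.

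Section 4.4.6.1 lists disease progression among the situations in which a patient may be taken off treatment, and then adds: "Patients may continue to receive study treatment following objective progression provided that, in the opinion of the Investigator, the patient is benefiting". The patient must also meet no other discontinuation criterion. The same section covers one route onto monotherapy: "In the event that cisplatin is permanently discontinued on the basis of cisplatin related toxicity, treatment with AZD2281 alone may continue", with possible escalation to 400 mg bid.

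Two other places tie follow-up to treatment. Table 4 footnote h says "Routine safety visits will be performed until discontinuation", and its original monotherapy interval is "patients should have weekly visits for the first two months (8 weeks) of AZD2281 monotherapy, and then every month (4 weeks"). After data cut-off, Section 6.6.1.1 requires visits at least every 8 weeks until a Section 4.4.6.1 criterion is met. Footnote h also provides that, once amendment 6 is approved, "patients on AZD2281 monotherapy can have their visit schedule modified as per Table 5 and Section 4.2.3".

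**The concern.** The rule for ending visits and the rule for ending treatment use different events. A site that follows Section 4.2.3 and footnote a as written may stop scheduled blood counts at progression in a patient who is still being dosed under the Section 4.4.6.1 note.

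That matters because Section 1.2.3 names bone marrow as the target organ of toxicity, Section 2 reports thrombocytopenia that is sometimes grade 3 or 4, and the monotherapy dose may be 400 mg bid. Under Section 5.10.3, deterioration in a protocol-mandated laboratory value is reported as an adverse event only if it meets a seriousness criterion or is the reason for stopping treatment. That reporting rule applies on every schedule and does not result from this wording, but it means that symptom-free falls in counts are seen mainly through visit samples.

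**Working it through.** The protocol states no figure to reproduce on this point. The check sets the stop rules side by side.

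| Place in the Protocol | What it governs | When it ends |
|---|---|---|
| Section 4.2.3 | Monotherapy safety visits, 6-weekly after day 43 | RECIST progression, or another discontinuation criterion |
| Table 5 footnote a | Monotherapy study visits | RECIST progression, or unacceptable toxicity |
| Table 5, tumour row and footnote d | RECIST scans | Disease progression |
| Table 5 grid | Laboratory tests, vital signs, AEs, dispensing every 6 weeks | Next column is treatment discontinuation |
| Section 4.4.6.1 note | AZD2281 dosing | May go on past progression |
| Table 4 footnote h | Routine safety visits | Discontinuation |
| Section 6.6.1.1 | Visits after data cut-off, at least 8-weekly | A Section 4.4.6.1 criterion |

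1. The scans have their own progression stop in the tumour row and footnote d. Footnote a speaks of study visits and Section 4.2.3 of safety assessments, so neither can be read as a rule about scans only.
2. The Section 4.4.6.1 note makes time on drug after progression possible. Neither Section 4.2.3 nor footnote a mentions that exception.
3. Between progression and discontinuation, footnote a taken literally therefore requires no visit. Table 5 has a discontinuation visit and a 30-day follow-up, but these come after the drug has stopped.
4. The grid suggests otherwise. Haematology and chemistry are marked in the 6-weekly column and at discontinuation, and so is dispensing. The text points two ways.
5. The window closes at data cut-off, because Section 6.6.1.1 then supplies an interval.

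**Size.** Scheduled visits = whole part of (weeks on drug after progression ÷ interval). The durations of 6, 12 and 24 weeks are assumptions.

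| Interval | 6 weeks | 12 weeks | 24 weeks |
|---|---|---|---|
| 6-weekly, Table 5 continued | 6/6 = 1 | 12/6 = 2 | 24/6 = 4 |
| 4-weekly, Table 4 footnote h after the first 8 weeks of monotherapy | 6/4 → 1 | 12/4 = 3 | 24/4 = 6 |
| Table 5 footnote a, literal | none required | none required | none required |

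The last row describes what the text requires. It does not predict that no visits would take place.

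**Resupply.** At 400 mg bid the daily dose is 800 mg, and 800/50 = 16 capsules of 50 mg a day. Over 6 weeks that is 16 × 42 = 672 capsules, over 12 weeks 16 × 84 = 1,344, and over 24 weeks 16 × 168 = 2,688. Some contact for dispensing is therefore to be expected.

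**The case against.** The strongest reply is that Table 5 should be read as a whole. Its grid runs from the 6-weekly column straight to discontinuation. The dispensing row is marked only on day 1, day 43, every 6 weeks and at discontinuation. Footnote e places dispensing after the other procedures, Section 4.5.11 has bottles returned at a scheduled visit, and Section 5.6.1 attaches bloods to each visit. A patient who keeps receiving drug would most naturally be seen and sampled every 6 weeks. This largely stands as evidence of intent, and it rules out the inference that patients treated past progression would go unseen. It does not remove the inconsistency: footnote a qualifies that same grid, and footnote e leaves the quantity dispensed to the site, so the dispensing rules alone fix no interval.

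It can also be said that Section 4.2.3 describes the usual case, in which progression ends treatment, and that the Section 4.4.6.1 note is an exception. That is fair, and the exception is what Section 4.2.3 and footnote a leave out.

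A reader might infer that Table 4 footnotes h and q directly contradict Table 5. The documents do not support this. Footnote h itself moves monotherapy patients to Table 5. Footnote q ("Until a patient is withdrawn from the treatment or the study the assessments should be carried out as in visits 9/10/11") is attached to the column for cycles 3, 4 and 5. For a patient who is moved, the stop rule changes between schedules; the two rules are not in force together. Footnote h and Section 6.6.1.1 are context showing that the protocol elsewhere follows treatment.

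Other cover remains. Adverse events are collected throughout treatment and for 30 days after it (Section 5.10.3), and bloods may be taken when clinically indicated (Section 5.6.1). Section 4.5.3.9 asks for weekly counts, but only once haematological toxicity has interrupted or delayed treatment for 2 weeks or more, so it does not replace routine sampling.

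**Conclusion.** The inconsistency is real and minor. Section 4.2.3 and Table 5 footnote a stop safety visits at progression, while Section 4.4.6.1 allows AZD2281 beyond it. Read literally, this leaves no required haematology or chemistry visit between progression and discontinuation, although the grid suggests that 6-weekly visits were meant.

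It reaches only patients on the Table 5 schedule who are treated past progression before data cut-off. The move to Table 5 is optional, and patients kept on Table 4 retain a stated interval. The group is probably small, but the protocol gives neither its number nor its duration. Section 4.5.2.2 makes the switch after cycle 6 conditional on no progressive disease. Whether that also bars treatment after a later progression is a separate question that this point does not need to settle, since patients whose cisplatin was stopped for toxicity reach monotherapy under Section 4.4.6.1.

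A reader might go further and conclude that dose finding or the safety dataset is compromised. It is not: DLTs are counted in cycle 1, so the MTD is untouched, and adverse event collection and the primary objective do not depend on this wording.

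**What to change.** In Section 4.2.3 and Table 5 footnote a, replace progression with discontinuation of AZD2281 as the end of the 6-weekly safety visits (haematology, chemistry, vital signs, adverse events and dispensing). Keep progression as the end point for the RECIST tumour assessments only. This brings the text into line with the Table 5 grid.

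The cost is two wording changes and about two routine visits per 12 weeks (12/6 = 2) for each patient still on drug after progression. Where sites already follow the grid, nothing is added.

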## **4.3 Rationale and risk/benefit assessment**

### **4.3.1 Rationale for study design, doses and control groups**

This is a Phase I non-randomised, open label, dose finding study, to determine the maximum tolerated dose of AZD2281 that can be combined with cisplatin in patients with advanced solid tumours.

This study is designed to provide safety and tolerability data for AZD2281 in combination with cisplatin and PK data for AZD2281 alone and in combination with cisplatin.

For the continuous dosing combination treatment regimen, patients will attend the clinic 1 week (4-7 days) before the combination treatment is due and a single dose of AZD2281 will be given (dose depending on cohort recruited into). Plasma PK samples will be obtained over 12 hours. A PK profile will be again taken on day 1 of cycle 1 of cisplatin (day 8) when AZD2281 will be given in the presence of cisplatin. This will permit a comparison of the exposure to AZD2281 when given with cisplatin and without. Patients will be closely monitored for safety and dose levels will be assessed once at least 3 evaluable patients have completed 21 days of combination treatment or have experienced a DLT.

For intermittent dosing cohorts, no PK is required; therefore patients are only required to start their AZD2281 dosing on the same day as cisplatin is administered, unless a different dose schedule is advised by the safety monitoring committee.

The dose levels of 50, 100, 200 and 400 mg (twice-daily) either continuous or intermittent have been chosen, as previous Phase I studies have demonstrated that they are all generally well tolerated, yield systemic concentrations of AZD2281 and are likely to be biologically active.

The Phase I study design takes into account patient population, the emerging toxicity profile of AZD2281, pharmacology of cisplatin and potential for interactions that might impart treatment related toxicities. There is little evidence to suggest that there will be an ADME based interaction when the two drugs are administered in combination.

The number of patients is based on the desire to gain adequate information whilst exposing as few patients as possible to the study medication and procedures.

## **4.4 Selection of study population**

### **4.4.1 Study selection record**

Investigator(s) must keep a record of subjects who were considered for enrolment but never enrolled eg, subject screening log, according to local procedures. This information is necessary to establish that the subject population was selected without bias

Each patient should meet all of the inclusion criteria and none of the exclusion criteria for this study. Under no circumstances can there be exceptions to this rule.

#### 4.4.2 Inclusion criteria

For inclusion in the study patients must fulfil all of the following criteria:

1. Fully-informed written consent.
2. Adequate bone marrow, hepatic and renal function including the following:
  - Haemoglobin  $\geq 9.0$  g/dL
  - White blood cell count (WBC)  $> 3 \times 10^9/L$
  - Absolute neutrophil count (ANC)  $\geq 1.5 \times 10^9/L$
  - Platelet count  $\geq 100 \times 10^9/L$ ;
  - Total bilirubin  $\leq 1.5$  x institutional upper limit of normal (ULN);
  - AST (SGOT), ALT (SGPT)  $\leq 2.5$  x institutional upper limit of normal unless liver metastases are present in which case it must be  $\leq 5$ x ULN
  - Serum creatinine  $\leq 1.5$  mg/dL x institutional upper limit of normal (ULN)
  - Creatinine Clearance  $> 50$  mL/min (calculated or 24 hour urine sample)
3. Male or female patients, age  $\geq 18$  years
4. Performance status (PS)  $\leq 2$  (ECOG scale) (see [Appendix F](#))
5. The patient is willing and able to comply with the protocol for the duration of the study, including hospital visits for treatment and scheduled follow-up visits and examinations.
6. Negative pregnancy test for women of childbearing potential only.
7. Histologically confirmed metastatic cancer, not amenable to surgery or radiation therapy with curative intent for whom no standard (or approved) therapy is available.
8. Life expectancy of at least 12 weeks.
9. Patients with measurable or non measurable disease according to RECIST (see [Appendix D](#))

For inclusion in the genetic component of the study, patients must fulfil the following criterion:

- Provision of informed consent for genetic research

If a patient declines to participate in the pharmacogenetic component of the study, there will be no penalty or loss of benefit to the patient. The patient will not be excluded from other aspects of the study described in this Clinical Study Protocol, so long as they consent.

#### **4.4.3 Exclusion criteria**

Any of the following is regarded as a criterion for exclusion from the study:

1. Major surgery within 4 weeks of starting the study
2. Co-existing active infection
3. Gastrointestinal disorders likely to interfere with absorption of the study drug (eg, partial bowel obstruction, malabsorption) or with the patient's ability to take regular oral medication
4. Patients requiring treatment with inhibitors or inducers of CYP3A4 (see 4.5.10 for guidelines and wash out periods)
5. Patients currently experiencing seizures or who were currently being treated with any anti-epileptic for seizures (use of anti-epileptic drugs to control pain is allowed in patients not suffering from seizures unless drug is excluded due to CYP3A4 induction – phenytoin, carbamazapine, phenobarbitone (see Section 4.5.10).
6. Patients who are unable to swallow oral medication
7. A positive pregnancy test. Pregnant or breast-feeding women or women of childbearing potential unless effective methods of contraception are used (lack of childbearing potential is met by being post-menopausal, being surgical sterile, practicing contraception with an oral contraceptive or other hormonal therapy [eg, hormone implants], intra-uterine device, diaphragm with spermicide or condom with spermicide, or being sexually inactive. Patients and their partners must agree to use two of the above forms of contraception throughout the treatment period and for 3 months after discontinuation of treatment. Male patients must refrain from fathering a child or donating sperm during the study and for 3 months following the last dose of AZD2281.
8. Renal dysfunction for which exposure to cisplatin would require dose modification or be completely unsafe (serum creatinine >1.5 mg/dL)
9. Immunocompromised patients eg, Patients who are known to be serologically positive for human immunodeficiency virus (HIV).
10. Patients with active or severe cardiovascular or pulmonary disease, including recent (<6 months) myocardial infarction or deep-venous thrombosis/pulmonary embolism, congestive heart failure, uncontrolled hypertension (systolic blood

pressure >180 mm Hg, diastolic blood pressure >105 mm Hg), or steroid-dependent asthma, are ineligible.

11. Patients with peripheral neuropathy of any etiology that exceeds grade 1 (see [Appendix B](#)) are ineligible
12. Patients with uncontrolled diabetes (fasting blood sugar >200 mg/dL) are ineligible
13. Any co-existing medical condition that in the investigator's judgement will substantially increase the risk associated with the patient's participation in the study e.g. patients with a clinically significant hearing impairment
14. Simultaneous participation in any other study involving an investigational medicinal product, or having participated in a study less than 28 days prior to the start of study treatment.
15. Patients considered a poor medical risk due to a serious, uncontrolled medical disorder, non-malignant systemic disease. Examples include, but are not limited to, uncontrolled ventricular arrhythmia, uncontrolled major seizure disorder, unstable spinal cord compression, superior vena cava syndrome, or any psychiatric disorder that prohibits obtaining informed consent.
16. Prior use of any PARP inhibitor, including AZD2281, and any known hypersensitivity to AZD2281 or any of its excipients, cisplatin or other platinum containing compounds
17. Use of live virus vaccinations within 3 months before or after treatment
18. Less than 28 days from active therapy (i.e. any treatment used to treat the disease) or high dose radiotherapy (patients may continue concomitant use of a stable dose of bisphosphonates if used for at least 28 days prior to commencing study treatment and patients may receive palliative radiotherapy for bone disease during the study)
19. Brain metastases or spinal cord compression, unless irradiated at least 4 weeks before entry and stable without steroid treatment for  $\geq 1$  week.
20. Persistent CTCAE grade 2 or greater toxicities (excluding alopecia) caused by prior therapy

Procedures for withdrawal of incorrectly enrolled patients see Section [4.4.4](#).

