In the embryofoetal development study in the rat, administration of AZD2281 to female rats during the period of major embryonic organogenesis at a dose of 0.5 mg/kg resulted in slight maternal toxicity. There was no effect on pregnant animals after dosing with 0.05 mg/kg/day. After dosing with 0.5 mg/kg/day, early embryofoetal survival and foetal weights were reduced with the occurrence of major eye and vertebral/rib malformations and increased incidences of several visceral and skeletal minor abnormalities and variants. After dosing with 0.05 mg/kg/day, there was an associated increased incidence in a minor visceral abnormality and skeletal variant. There was also one foetus with a major eye malformation. A “no observed adverse effect” dose level for foetal abnormalities was not established.

Further information can be found in the current version of the olaparib Investigator’s Brochure.

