##### **4.4.5.1 Contraception**

Patients of child bearing potential and their partners, who are sexually active, must agree to the use of two highly effective forms of contraception throughout their participation in the study and for 3 months after last dose of study drug(s).

- Condom with spermicide

and one of the following

- Oral contraceptive or hormonal therapy (e.g. hormone implants)
- Placement of an intra-uterine device

Acceptable non-hormonal birth control methods include:

- Total sexual abstinence. Abstinence must be for the total duration of the study and the drug washout period.
- Vasectomised sexual partner plus male condom. With participant assurance that partner received post-vasectomy confirmation of azoospermia
- Tubal occlusion plus male condom with spermicide
- Intrauterine Device (IUD) plus male condom+spermicide. Provided coils are copper-banded

Acceptable hormonal methods:

- Etonogestrel implants (eg, Implanon, Norplan)+male condom with spermicide
- Normal and low dose combined oral pills+male condom with spermicide

- Norelgestromin/ethinyl estradiol (EE) transdermal system+male condom with spermicide
- Intravaginal device+male condom with spermicide (eg, EE and etonogestrel)
- Cerazette (desogestrel)+male condom with spermicide. Cerazette is currently the only highly efficacious progesterone based pill.

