## **5.6.2 Other Safety Assessments**

### **5.6.2.1 Serum or urine pregnancy test**

Two pregnancy tests on blood or urine samples will be performed for pre-menopausal women of childbearing potential one within 28 days prior to the start of study treatment and the other on Day 1 of the study prior to commencing treatment. Tests will be performed by the hospital's local laboratory. If results are positive the patient is ineligible/must be discontinued

from the study. In the event of a suspected pregnancy during the study, the test should be repeated.

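### Exclusion 7 counts contraceptive use and sexual inactivity as lack of childbearing potential, which read literally leaves fertile women without the Day 1 pregnancy test and contradicts section 4.4.5.1

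*Protocol*

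**What the plan says.** **Definition.** Exclusion 7 (section 4.4.3) bars women of childbearing potential who do not use effective contraception. A parenthesis then explains the term: "lack of childbearing potential is met by being post-menopausal, being surgical sterile, practicing contraception with an oral contraceptive or other hormonal therapy". After an example of hormonal therapy, the same list continues with "intra-uterine device, diaphragm with spermicide or condom with spermicide, or being sexually inactive".

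**Two-method rule in the same criterion.** The next sentence reads "Patients and their partners must agree to use two of the above forms of contraception throughout the treatment period" and for 3 months after treatment is discontinued. It is not limited to women of childbearing potential.

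**Pregnancy test.** Inclusion 6 (section 4.4.2) asks for "Negative pregnancy test for women of childbearing potential only". The screening list (4.2.1) and the on-trial list (4.2.2) carry the same condition. Section 5.6.2.1 and Table 4 footnote f state "Two pregnancy tests on blood or urine samples will be performed for pre-menopausal women of childbearing potential", one within 28 days before treatment and one on Day 1 before dosing. Table 9 lists a urine human gonadotrophin test whose footnote assigns it to premenopausal women, pre-study only, with no reference to childbearing potential.

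**Contraception section.** Section 4.4.5.1 says "Patients of child bearing potential and their partners, who are sexually active, must agree to the use of two highly effective forms of contraception". It pairs a condom with an oral contraceptive, other hormonal therapy or an IUD, and separately accepts total abstinence.

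**The concern.** Childbearing potential decides who is tested for pregnancy and, in section 4.4.5.1, who must use two methods. Exclusion 7 is the only place where the protocol says what lack of that potential means, and its wording mixes two things: states in which a woman cannot conceive, and behaviour that makes conception less likely. Using a contraceptive method is what the criterion demands of women who can conceive. Listing it as proof that they cannot conceive removes them from the group that the test is meant to protect.

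The stakes come from the protocol's own toxicology summary (section 1.2.3). In the rat embryofoetal study there were major eye and vertebral or rib malformations at 0.5 mg/kg/day, and one foetus with a major eye malformation at 0.05 mg/kg/day. The section concludes that a no-effect "dose level for foetal abnormalities was not established". It also reports that AZD2281 was clastogenic in vitro and genotoxic in the rat micronucleus test.

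The literal wording matters because sections 4.4.1 and 4.4.4 allow no exceptions to the selection criteria.

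**Working it through.** No arithmetic applies. The check carries the definition in exclusion 7 through each provision that depends on it.

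**Step 1: does the definition agree with itself?** The opening clause of exclusion 7 supposes women of childbearing potential who use effective contraception and may therefore enter. Under the parenthesis no such woman exists, because using a listed method already places her outside the category. The clause is circular.

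**Step 2: does it agree with section 4.4.5.1?** That section addresses patients of childbearing potential and prescribes, for them, a condom plus the pill, other hormonal therapy or an IUD. Women on those methods are of childbearing potential there and lack it in exclusion 7.

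**Step 3: who is tested under the literal definition?** Divide premenopausal women who are not surgically sterile into three groups:

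- (a) using a listed method: lacking childbearing potential under the parenthesis;
- (b) sexually inactive: likewise;
- (c) sexually active and using no method: of childbearing potential, but barred by exclusion 7 unless they begin a method, which moves them to (a).

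| Provision | Condition for the test | Reaches (a) and (b)? |
|---|---|---|
| Inclusion 6 | childbearing potential | No |
| 4.2.1, screening list | childbearing potential | No |
| 4.2.2, on-trial list | childbearing potential | No |
| Table 4 footnote f, screening and Day 1 | premenopausal and childbearing potential | No |
| 5.6.2.1, screening and Day 1 | premenopausal and childbearing potential | No |
| Table 9 footnote a, pre-study urine gonadotrophin | premenopausal | Yes |

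Five of the six provisions miss groups (a) and (b). The sixth reaches them before the study only. No provision gives them the Day 1 test. Table 9 itself is not fully supported elsewhere: section 5.6.2.2 describes urinalysis as a dipstick for blood, protein and glucose and does not mention gonadotrophin.

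**Step 4: the contraception rules side by side.**

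| Feature | Exclusion 7 | Section 4.4.5.1 |
|---|---|---|
| Who must use two methods | all patients and their partners | sexually active patients of childbearing potential and their partners |
| Diaphragm | listed | not listed |
| Condom | one option among several | part of every pairing |
| Sexual inactivity or abstinence | listed as lack of childbearing potential | accepted as a birth control method |

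The two sections differ on scope and on methods. A pill with a diaphragm satisfies the words of exclusion 7 but not section 4.4.5.1.

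**The case against.** The best reply is that the rest of the protocol uses the term in its ordinary sense. Section 4.4.5.1 does, section 5.6.2.1 and Table 4 footnote f pair it with premenopausal status, and section 9.4.1 foresees pregnancy in a woman whose contraceptive may have been made less effective by study medication. On this view the parenthesis is a badly worded list of ways to be eligible, and most sites would test these women anyway. That is probably how it would work in practice, but a criterion that gives the intended result only when staff disregard its words still needs correcting, above all where no exceptions are allowed. The contrast with the other sections confirms the contradiction.

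On the method lists, it can fairly be said that a patient has to satisfy both sections, and that a condom with the pill or an IUD does so. That stands: the differing lists are inconsistent drafting and do not by themselves remove a safeguard.

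Two stronger readings are tempting, and the protocol does not support them:

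- **That exclusion 7 frees contraceptive users from the two-method rule.** It does not. Its next sentence binds all patients and their partners. An exemption appears only if the definition is carried into section 4.4.5.1 and that sentence is ignored. What remains is a contradiction about scope.
- **That nobody is left to be tested.** Table 9 gives premenopausal women a pre-study gonadotrophin test whatever their contraceptive use, and exclusion 7 bars any patient with a positive pregnancy test. The literal gap lies in the other five provisions and is complete only for Day 1.

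**Conclusion.** The definition in exclusion 7 is wrong as written. It is circular within the criterion, contradicts section 4.4.5.1 and, taken literally, removes fertile women who use a method or are sexually inactive from five of the six pregnancy-test provisions. The pre-study test in Table 9 remains; the Day 1 test does not. The rules on who must use two methods, and which ones, also conflict between exclusion 7 and section 4.4.5.1.

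The conclusion assumes that the definition in exclusion 7 is the one that sites apply to the term elsewhere; the protocol gives no other. The number of women affected cannot be stated: about 60 patients of either sex are expected, and the protocol gives no figure for premenopausal women among them.

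The point concerns maternal and foetal safety only. It does not affect the assessment of dose-limiting toxicity, the maximum tolerated dose, the sample size or any analysis.

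**What to change.** Reword the parenthesis in exclusion 7 so that using contraception or being sexually inactive is not in itself stated as lack of childbearing potential.

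Then reconcile Inclusion 6, exclusion 7, sections 4.2.1, 4.2.2, 4.4.5.1 and 5.6.2.1, Table 4 footnote f and Table 9 footnote a on four questions:

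1. who counts as of childbearing potential;
2. who is tested for pregnancy, and when;
3. to whom the two-method rule applies;
4. which list of methods applies.

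The sponsor decides the clinical content of the answers; this review does not prefer either list. The cost is amendment wording and an already scheduled pregnancy test in a few more women.
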